#### **4.2.6.2 Proportion of responders by PRO measures**

Responder at the post-baseline visit from the selected secondary endpoints below will be analyzed using a logistic regression model with repeated measures using generalized equation estimate method. The model will include treatment, region, visit and treatment group by visit interaction as fixed factors, and baseline scores as a covariate. The variance-covariance matrix will be assumed to be unstructured.

ACQ-6 responder at each post-baseline visit: Will be based on change from baseline to each post-baseline visit as defined in Section 3.3.2. Patients with missing or non-evaluable score at a post-baseline visit will be considered non-responders.

SGRQ responder at each post-baseline will be defined for each post-baseline visit as an individual with a  $\geq 4$ -point decrease (improvement) from baseline in SGRQ total score. Patients with missing or non-evaluable score at any post-baseline visit will be considered non-responders.

#### **4.2.7 Exploratory efficacy outcome variable**

##### **4.2.7.1 Exploratory analysis of PGI-S**

The same analysis approach described in the primary analysis will be performed on the change from baseline in PGI-S at each post-baseline visit. A summary table will be produced showing the number and percentage of patients with improvement from baseline at each post-baseline visit.

Patients with a PGI-S improvement at the EOT visit will be analyzed using a logistic regression model with covariates of treatment and region.

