## 1.3 Number of subjects

The study will recruit approximately 230 patients in total and 115 patients in each treatment group based on the primary objective of the study to determine the effect of benralizumab on the time course of change (onset and maintenance of effect) of pre-bronchodilator (BD) FEV1.

Patients will be randomized in a 1:1 ratio to benralizumab or placebo. In order to have a balanced number of patients for each region and the body plethysmography sub-study, the randomization will be stratified by these variables.

The study is powered for the primary objective of the study to determine the effect of benralizumab on the time course of change (onset and maintenance of effect) of pre-BD FEV1.

The first post-baseline timepoint where the p-value for the mean difference between benralizumab and placebo is  $\leq 0.05$  will be used to determine time to onset of effect. The average over the mean differences between benralizumab and placebo based on the change from baseline (Visit 4) to Days 28 (Visit 8), 56 (Visit 9), and 84 (Visit 10) in pre-BD FEV1 will be used to determine if the study is positive and to determine maintenance of effect.

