The results of the Phase 2b study, MI-CP220 (Castro et al 2014) and the Phase 3 asthma exacerbation studies, SIROCCO (Bleeker et al 2016) and CALIMA (Fitzgerald et al 2016) were used as a basis for the sample sizing. From these studies, it is expected that around 115 patients per treatment arm (230 in total) will provide approximately 90% power for the primary endpoint pre-BD FEV1 with type I error controlled at a two-sided alpha level of 0.05 if the true average over the mean treatment differences (benralizumab – placebo) across Days 28 (Visit 8), 56 (Visit 9), and 84 (Visit 10) is 138 mL. The sample size will also be sufficient to have approximately 80% power for an average over the mean treatment difference of 120 mL. The assumed variability has a within-group standard deviation of 375 mL and within-patient correlation of 0.6. If the within-patient variability is reduced to 350 mL, the sample size would be sufficient 80% power for an average of 110 mL. In addition, it is expected that around 115 patients per treatment arm will have 80% power to detect a true treatment difference (benralizumab – placebo) of 130 mL, assuming a within-group standard deviation of 350 mL or a true treatment difference of 140 mL, assuming a standard deviation of 375 mL. Based on these assumptions, the minimum difference that would be statistically significant at the 5% level ranges from approximately 85 to 100 mL. The sample size was estimated using nQuery + nTerim version 3.0 using methodology by Liu et al (Liu et al 2005).

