ACQ-6, SGRQ, and PGI-S assessments at Week 0 (Visit 4) prior to randomization will be used for calculating the respective baselines. For ACQ-6, if the value at Week 0 (Visit 4) is missing, the non-missing value from Day -35 (Visit 1) will be used for baseline.

For summaries of vital signs and laboratory results by visit and in the calculation of change from baseline, the last non-missing assessment prior to first dose of study treatment will be used as baseline.

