##### **4.2.7.2 Exploratory analysis of CGI-C and PGI-C**

The CGI-C and PGI-C responses will be summarized by treatment group and visit. The number and percentage of patients will be presented for CGI-C, PGI-C, and for agreement in CGIC and PGIC responses as described in Section 3.3.2.

The number and percentage of patients defined as responders based on categorized responses for CGI-C and PGI-C (improved, much improved, very much improved) will also be presented by treatment group and visit.

Responders at the EOT visit will be analyzed using a logistic regression model with covariates of treatment and region.

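### The PGI-S improvement model leaves out baseline PGI-S, which decides who can respond and is already collected; the test stays valid but loses some precision

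*SAP*

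**What the plan says.** SAP section 4.2.7.1 contains two PGI-S analyses. The first takes change from baseline at each visit and follows the primary analysis approach, which in section 4.2.5.1 is an MMRM with the baseline value as a covariate. The second dichotomises: "Patients with a PGI-S improvement at the EOT visit will be analyzed using a logistic regression model with covariates of treatment and region". Section 4.2.7.2 does the same for the two global impressions of change: "Responders at the EOT visit will be analyzed using a logistic regression model with covariates of treatment and region".

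The responder models for ACQ-6 and SGRQ in section 4.2.6.2 are fuller: "The model will include treatment, region, visit and treatment group by visit interaction as fixed factors, and baseline scores as a covariate". They are repeated-measures logistic models over all post-baseline visits.

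The baseline value is available. SAP section 2.2.3 states: "ACQ-6, SGRQ, and PGI-S assessments at Week 0 (Visit 4) prior to randomization will be used for calculating the respective baselines". CGI-C and PGI-C rate change since randomization (section 3.3.2) and have no baseline score of their own.

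SAP section 3.3.1 describes PGI-S improvement as a move from moderate, severe or very severe to mild, very mild or no symptoms. Protocol section 8.4.1.7 is wider and also counts patients whose response improves from baseline.

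Protocol section 8.5.2.1 gave all five responder variables the same treatment-and-region model. The SAP added the baseline score for ACQ-6 and SGRQ only, and SAP section 6 does not list that change.

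**The concern.** Under the SAP's description of improvement, the starting category determines whether a patient can respond at all. Patients at mild or better at Visit 4 are non-responders by construction in both arms. Among the rest, a patient at very severe has further to move than one at moderate. The chance of response is therefore zero at the low end of the scale, highest near moderate, and lower again at the severe end.

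Entry does not remove the patients who cannot respond. The protocol's Visit 4 criteria require an ACQ score above 0.75, and PGI-S is not an eligibility criterion.

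A model with treatment and region alone treats all this variation as noise. At stake is precision in the PGI-S responder comparison and protection against a chance imbalance in starting severity. The SAP makes that adjustment for the same instrument analysed as a continuous score, and gives no reason for dropping it here.

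**Working it through.** **Inputs from the documents.** Allocation: "Patients will be randomized in a 1:1 ratio to benralizumab or placebo". There are 115 patients per arm, with "type I error controlled at a two-sided alpha level of 0.05". No PGI-S response rate, baseline distribution or correlation is given.

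**The plan's own power figure.** The only stated power is for FEV1: "it is expected that around 115 patients per treatment arm (230 in total) will provide approximately 90% power", for a time-averaged difference of 138 mL. "The assumed variability has a within-group standard deviation of 375 mL and within-patient correlation of 0.6".
- Effective SD over three visits = 375 × √((1 + 2 × 0.6)/3) = 375 × 0.856 = 321 mL.
- Standard error = 321 × √(2/115) = 42.3 mL.
- Power = Φ(138/42.3 − 1.96) = Φ(1.30) = 90.3%.

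The figure reproduces. It fixes n and alpha but says nothing about PGI-S.

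**PGI-S simulation (all clinical inputs assumed).** Baseline and EOT severity are correlated normal variables cut into six categories. Both arms shift by 0.4 SD towards improvement and the active arm by a further 0.4 SD. Response follows the SAP description. There are three equal regions, a two-sided Wald test at 0.05 and 1500 runs per row, so each power has a standard error of about √(0.5 × 0.5/1500) = 1.3 points.

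| Baseline assumed (share at mild or better) | Correlation | No baseline | Linear | Linear + quadratic |
|---|---|---|---|---|
| Mostly moderate (25%) | 0.3 | 48.8% | 49.8% | 55.3% |
| | 0.5 | 52.1% | 52.5% | 59.7% |
| | 0.7 | 58.6% | 58.9% | 69.2% |
| Milder (45%) | 0.3 | 27.9% | 34.6% | 41.8% |
| | 0.5 | 31.7% | 39.0% | 47.7% |
| | 0.7 | 42.4% | 46.0% | 62.7% |
| Severe (10%) | 0.3 | 54.8% | 54.7% | 56.7% |
| | 0.5 | 54.7% | 54.7% | 58.0% |
| | 0.7 | 59.5% | 61.4% | 66.7% |

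In this table the linear term gains from −0.1 to +7.3 points, and linear plus quadratic from +1.9 to +20.3. A separate run of the same kind gave about 0 to 8 and 2 to 17. Taken together the ranges are about 0 to 8 and 2 to 20. The quadratic term matters because response rises and then falls with baseline severity.

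**Effect of patients who cannot respond.** Assume 45% v 63% response among those able to respond, and a fraction f at mild or better. Power = Φ[(d − 1.96√(2p̄(1−p̄)/n)) / √((p₁(1−p₁)+p₂(1−p₂))/n)], where d = p₂ − p₁ and p̄ is the mean of the two rates. For f = 20%:
- All patients: 0.8 × 45% = 36.0% v 0.8 × 63% = 50.4%, n = 115. Power = Φ((0.144 − 0.128)/0.0646) = Φ(0.25) = 60%.
- Able to respond only: 45% v 63%, n = 0.8 × 115 = 92. Power = Φ((0.180 − 0.144)/0.0723) = Φ(0.50) = 69%.

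The same formula gives 69% v 74% at f = 10% and 50% v 63% at f = 30%.

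**If any decrease counted as improvement**, as part of the protocol wording allows, a linear term would add about 2 to 12 points under the same assumptions.

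**The case against.** The case for leaving the model alone has real force.

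- PGI-S already has a baseline-adjusted analysis, the continuous one in the same section. The logistic model is an additional dichotomised look at EOT. This stands and limits the consequence.
- The treatment-and-region model follows the protocol. The SAP's departure is in ACQ-6 and SGRQ, where baseline was added. This also stands, but it does not explain why one set of responder variables was upgraded and the other not.
- The endpoints are exploratory (SAP section 1.1.4), their p-values are nominal (section 4.1), and no power is claimed for them. This stands.

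A reader might also infer more than the documents support.

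- *That the unadjusted odds ratio is biased or the test invalid.* It is neither. Randomization protects the test. The unadjusted odds ratio usually lies nearer 1 than the baseline-adjusted one because it is a marginal rather than a conditional quantity.
- *That a definite 7 to 9 points of power are lost.* Such figures come from assuming a conditional log odds ratio of 0.75 for treatment and a constant 0.8 or 1.2 per SD of baseline (70% v 77% and 62% v 71%). None of these values is in the documents, and a constant slope does not fit a threshold definition. Even in that generic form, with 45% v 63% response, the change is nil if baseline is not prognostic (79.9% v 79.5%), and about 10 points only at 1.5 per SD (81.1% v 91.4%).
- *That power is lost relative to the ACQ-6 and SGRQ models.* Those are different endpoints and use all visits, so no such comparison isolates the baseline term. They show an inconsistency in approach only.
- *That CGI-C and PGI-C have the same defect.* They have no baseline of their own, so the parallel does not carry over directly.

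**Conclusion.** The point holds as a small, low-cost improvement to one exploratory model. The PGI-S improvement analysis omits a baseline value that the trial collects, that the SAP uses elsewhere, and that under the SAP's description determines who can respond. The comparison remains valid and the cost is precision.

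The stated gains depend on the assumed baseline distributions, the assumed correlations of 0.3 to 0.7, and reading the SAP's description of improvement as complete. They are largest where many patients start at mild or better, and near zero for a linear term where few do. For CGI-C and PGI-C, adjustment by a borrowed baseline is an option, with a gain that may be zero. No confirmatory conclusion of the trial is affected.

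**What to change.** In SAP section 4.2.7.1, add baseline PGI-S to the improvement model with linear and quadratic terms. Alternatively, fit the model only in patients at moderate or worse at Visit 4, with baseline PGI-S as a covariate. Restricting on a pre-randomization value keeps the randomized comparison intact. A fully categorical baseline term should be avoided in the all-patient model, because the categories at mild or better contain no responders. State the numeric coding as well: protocol section 8.4.1.7 runs the six-point scale from 0 to 5, while SAP section 3.3.1 labels its upper end 6.

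Optionally, add one named baseline severity measure, for example ACQ-6, to the CGI-C and PGI-C models in section 4.2.7.2, or say why none is used. List the added baseline covariate for the ACQ-6 and SGRQ responders in SAP section 6.

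The cost is one or two model terms and no new data. No patient is lost from the PGI-S model, since improvement already requires a baseline value. The odds ratio becomes conditional on baseline and is not directly comparable with an unadjusted one. Under the restricted option it applies only to patients able to respond.

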##### **4.2.7.2 Exploratory analysis of CGI-C and PGI-C**

The CGI-C and PGI-C responses will be summarized by treatment group and visit. The number and percentage of patients will be presented for CGI-C, PGI-C, and for agreement in CGIC and PGIC responses as described in Section 3.3.2.

The number and percentage of patients defined as responders based on categorized responses for CGI-C and PGI-C (improved, much improved, very much improved) will also be presented by treatment group and visit.

Responders at the EOT visit will be analyzed using a logistic regression model with covariates of treatment and region.

#### **4.2.8 Sub-study body plethysmography outcome variable**

The objective of the sub-study is to determine the effect of benralizumab on the time course of change (onset and maintenance of effect) of body plethysmography outcome variables. Only the outcome values with acceptable quality (acceptable or borderline quality grade) will be used for analyses. All the observed and change from baseline of sub-study variables will be summarized by treatment and visit.

#### **4.2.8.1 Sub-study primary analysis**

The change from baseline in RV at each timepoint will be compared between benralizumab and placebo using an MMRM analysis in the sub-study population if sufficient acceptable quality data warrants.

The dependent variable will be the change from baseline in RV at post-baseline protocol specific visits (up to and including the EOT Visit). Treatment group will be fitted as the explanatory variable, visit and treatment\*visit interaction as fixed effects, and baseline RV will be fitted as a covariate. Region may be fitted as a fixed effect. The variance-covariance matrix will be assumed to be unstructured. If the procedure does not converge, then a compound symmetric variance-covariance matrix will be used instead.

As for the primary efficacy analysis, contrasts will be used to obtain estimates of the treatment differences over Days 28, 56, and 84 as well as at each timepoint separately. Results will be presented in terms of LSMEANS, treatment differences in LSMEANS, 95% CIs of treatment differences, and p-values at each planned timepoint.

#### **4.2.8.2 Sub-study secondary analysis**

The change from baseline at each timepoint for TLC, ratio TLC/RV, VC, IC and FRC may be compared between benralizumab and placebo using an MMRM analysis in the sub-study population as for the primary efficacy analysis of sub-study as described above.

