3.1 Inclusion criteria

For inclusion in the study subjects should meet the following criteria:

1. Written informed consent for study participation must be obtained prior to any study related procedures being performed and according to international guidelines and/or applicable European Union (EU) guidelines.
2. Female and male aged 18 to 75 years inclusively at the time of Visit 1
3. Documented current treatment with ICS and LABA for at least 30 days prior to Visit 1.
 - For ICS/LABA combination preparations, high-strength maintenance doses approved in the given country will meet this criterion.

- If the ICS and LABA therapies are given by separate inhalers, the ICS dose must be >500 µg fluticasone propionate dry powder formulation or equivalent daily (see [Appendix F](#)).
- Additional asthma controller medications, eg, oral corticosteroids, long-acting anti-muscarinics (LAMAs), LTRAs, theophylline etc. are allowed if they have been used for at least 30 days prior to Visit 1.
- 4. History of at least 2 asthma exacerbations that required treatment with systemic corticosteroids (intramuscular (IM), intravenous (IV), or oral) in the 12 months prior to Visit 1. For patients receiving corticosteroids as a maintenance therapy, the corticosteroid treatment for the exacerbation is defined as a temporary increase of their maintenance dose.
- 5. Pre-bronchodilator (pre-BD) FEV₁ of < 80% predicted at Visit 2 or Visit 3
- 6. ACQ-6 score ≥1.5 at Visit 1
- 7. Evidence of asthma as documented by airway reversibility (FEV₁ ≥12% and 200 ml) demonstrated at Visit 1, Visit 2 or Visit 3 (as described in Section 5.1.1.1). For patients entering the body plethysmography sub-study, reversibility must be demonstrated at Visit 1 or at Visit 2 only.
- 8. Peripheral blood eosinophil count of ≥300 cells/µL assessed by central lab at Visit 1
- 9. Women of childbearing potential (WOCBP) must use an effective form of birth control (confirmed by the Investigator), eg, true sexual abstinence, a vasectomized sexual partner, Implanon®, female sterilization by tubal occlusion, any effective IUD Intrauterine device/IUS levonorgestrel Intrauterine system, Depo-Provera™ injections, oral contraceptive, and Evra Patch™ or Nuvaring™. WOCBP must agree to use birth control, as defined above, from enrolment, throughout the study duration and until 16 weeks after last dose of investigational product (IP). WOCBP must also have negative serum pregnancy test result on Visit 1.

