3.1.1 Additional inclusion criteria applicable for the Body Plethysmography sub-study

1. Residual volume $\geq 125\%$ of predicted at Visit 3.

Patients who do not meet this criterion and/or are not able to take body plethysmography assessments, should continue in the main study only.

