8.4.2 Body plethysmography sub-study

8.4.2.1 Body lung function as assessed through body plethysmography

The mean change from baseline to each of the post-randomization visits (post Visit 4) up to and including the end of 12-week double-blind treatment visit (Visit 10) will be used as efficacy variables within the body plethysmography sub-study analysis set. The level recorded at Visit 4 will be used as baseline. The primary variable for the sub-study will be the change from baseline in residual volume (RV). Secondary variables for the sub-study will be the change from baseline in total lung capacity (TLC), RV/TLC ratio, vital capacity (VC), inspiratory capacity (IC) and functional residual capacity (FRC). Other variables for the sub-study are SGaw and Raw.

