8.5.2.2 Analysis for the Body plethysmography sub-study

For the body plethysmography sub-study the primary efficacy variable is the change from baseline in body lung function RV as assessed through body plethysmography until EOT at Visit 10

Secondary efficacy variables for the body plethysmography sub-study are:

- Change from baseline in body lung function (TLC, RV/TLC ratio, VC, IC, and FRC) as assessed through body plethysmography until EOT at Visit 10

Other endpoints for the body plethysmography sub-study are change from baseline in SGaw and Raw.

These endpoints will be analysed as for the primary endpoint however in the subset of patients in the body plethysmography sub-study population.

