### **3.4.2 Secondary efficacy variables**

The secondary efficacy variables for the sub-study include the change from baseline in total lung capacity (TLC), ratio of RV/TLC, inspiratory capacity (IC), and functional residual capacity (FRC), vital capacity (VC).

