#### **4.2.8.3 Sub-study explorative analysis**

Only descriptive statistics for SGaw and Raw and change from baseline will be provided at each scheduled visit at which assessments are performed.

Subgroup analyses of RV and ratio TLC/RV may be performed for the age group categories (18-30 years, 31-65 years).

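### SAP 4.2.8.2 and 4.2.8.3 name the ratio TLC/RV where the defined sub-study endpoint is RV/TLC, and the optional age subgroups in 4.2.8.3 leave out ages 66-75

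*SAP*

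**What the plan says.** **Definition of the ratio.** SAP 3.4.2 lists the secondary sub-study variables, which "include the change from baseline in total lung capacity (TLC), ratio of RV/TLC" among others. The objectives table in SAP 1.1.5 has the same ratio. Protocol 8.4.2.1 reads "Secondary variables for the sub-study will be the change from baseline in total lung capacity (TLC), RV/TLC ratio, vital capacity (VC", and the protocol's sub-study analysis section, 8.5.2.2, reads "Change from baseline in body lung function (TLC, RV/TLC ratio, VC, IC, and FRC". The protocol synopsis and sections 1.3 and 2.6 agree.

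**Analysis of the ratio.** SAP 4.2.8.2 reads "The change from baseline at each timepoint for TLC, ratio TLC/RV, VC, IC and FRC may be compared between benralizumab and placebo", using the mixed model for repeated measures (MMRM) of the sub-study primary analysis. SAP 4.2.8.3 repeats the inverted form: "Subgroup analyses of RV and ratio TLC/RV may be performed for the age group categories (18-30 years, 31-65 years".

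**Age.** Protocol 3.1 admits patients as follows: "Female and male aged 18 to 75 years inclusively at the time of Visit 1". Protocol 3.1.1 adds only one criterion for the sub-study, a residual volume of at least 125% "of predicted at Visit 3". It sets no age limit.

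**Declared changes.** SAP section 6 lists one departure from the protocol, on ECG summaries. It mentions neither the ratio nor the age bands.

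**The concern.** The two SAP sections that say how the ratio is to be analysed name the reciprocal of the variable that the same SAP defines. The model in 4.2.8.1, which 4.2.8.2 borrows, is linear in the change from baseline, with the baseline value as covariate. A linear model of changes in 1/x is not a re-expression of a linear model of changes in x. The sign of benefit reverses, patients are weighted differently according to where they start, and estimate, interval and p-value all differ. If programming follows 4.2.8.2 as printed, the reported ratio result is not the endpoint that was defined. If it follows 3.4.2, it departs from the printed analysis. Leaving both in the plan leaves two non-equivalent analyses open.

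The age bands raise a separate and smaller matter. An exploratory subgroup analysis of RV and the ratio would have no place for part of the eligible population, and no reason is given.

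**Working it through.** **No plan figure to reproduce.** The documents give no power or effect-size figure for the sub-study, only a size of about 50 patients. The check is a comparison of texts, then arithmetic on assumed values.

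**1. Which ratio, where**

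| Place | Ratio |
|---|---|
| Protocol synopsis, 1.3, 2.6 | RV/TLC |
| Protocol 8.4.2.1 (variables) | RV/TLC |
| Protocol 8.5.2.2 (analysis) | RV/TLC |
| SAP 1.1.5 (objectives) | RV/TLC |
| SAP 3.4.2 (variables) | RV/TLC |
| SAP 4.2.8.2 (analysis) | TLC/RV |
| SAP 4.2.8.3 (age subgroups) | TLC/RV |

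The inversion appears only in the SAP analysis text, and there twice.

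**2. Effect of the inversion.** If RV/TLC falls from x to x − d, TLC/RV rises by 1/(x − d) − 1/x = d / [x(x − d)]. Take d = 0.05. The baselines are assumed, because the documents give no distribution of RV/TLC.

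- x = 0.40: 0.05 / (0.40 × 0.35) = 0.36
- x = 0.50: 0.05 / (0.50 × 0.45) = 0.22
- x = 0.60: 0.05 / (0.60 × 0.55) = 0.15

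The same change in the defined endpoint counts 0.33 / 0.14 = 2.4 times as much at 0.40 as at 0.60, and its sign is reversed.

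**3. Can it change a result?** An illustrative simulation used 25 patients per arm and 4,000 trials per scenario. Assumed values were mean TLC 6.5 L (SD 1.0), mean baseline RV/TLC 0.48 (SD 0.08), SD of RV change 0.5 L and SD of TLC change 0.3 L. Each ratio was analysed at a single visit by ANCOVA on change, two-sided 0.05, which simplifies the planned MMRM.

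| Assumed RV effect | Significant, RV/TLC | Significant, TLC/RV | Verdicts differ | Mean estimate, RV/TLC | Mean estimate, TLC/RV |
|---|---|---|---|---|---|
| 0 L | 4.9% | 4.6% | 3.6% | 0.000 | −0.002 |
| −0.2 L | 25% | 21% | 11% | −0.031 | +0.188 |
| −0.4 L | 74% | 64% | 16% | −0.063 | +0.419 |

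The two analyses mostly agree but are not interchangeable.

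**4. Age coverage.** Eligible single-year ages: 75 − 18 + 1 = 58. Covered by the two bands: 65 − 18 + 1 = 48. Uncovered: 58 − 48 = 10, namely 66 to 75. That is 10/58 = 17% of the age range, which is not a share of patients. The documents do not say how many sub-study patients fall there. If 5% to 15% of about 50 did (an assumption), the number would be 2.5 to 7.5, or roughly 3 to 8. The main-study age subgroups in SAP 4.2.5.3 (<65, ≥65) cover every age.

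**5. Who is in the models.** SAP 2.1.3 defines the sub-study set as those randomized into the sub-study who received any investigational product. SAP 4.2.8.1 and 4.2.8.2 use that set with no age restriction.

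**The case against.** The strongest reply is that this is a transposition which the documents resolve themselves. Every definition says RV/TLC, the protocol's analysis section says RV/TLC, and SAP 4.2.8 has all sub-study variables summarized by treatment and visit, with the variables defined in 3.4.2. The analyses concerned are conditional in the SAP, and SAP 4.1 makes every p-value outside the primary analysis nominal. RV, the sub-study primary variable, and the other four secondary variables (TLC, VC, IC, FRC) are unaffected. The numerical illustrations use invented baselines.

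Most of that stands, and it sets the scale of the point. It does not remove it. The slip occurs twice, in the text that specifies the model, and is not declared in section 6. An analysis that may be run still has to name the right variable, and protocol 8.5.2.2 plans the ratio analysis without the SAP's conditional wording. The direction of benefit reverses whatever the baselines are; only the size of the reweighting depends on them.

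A reader might infer that the sub-study secondary analysis is run on an incomplete population. The documents do not support that. The age bands are in 4.2.8.3 and not in 4.2.8.2, they govern only an optional exploratory subgroup, and patients aged 66-75 remain in the RV primary model and in every secondary model. What is missing for them is a subgroup estimate.

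**Conclusion.** The point holds as a contradiction within the SAP, and between the SAP and the protocol, in operative analysis text. SAP 4.2.8.2 and 4.2.8.3 name a quantity that is not equivalent to the defined endpoint and has the opposite direction of benefit. Its size is modest: one of five secondary sub-study variables, one conditional analysis and one exploratory subgroup. The 2.4-fold reweighting and the 11% to 16% discordance under the two nonzero effects rest wholly on assumed values and show only that the choice of ratio can matter.

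A reader might also conclude that a sub-study endpoint will be formally tested on the wrong quantity. That goes too far, because the comparison is optional in the SAP and any p-value is nominal. TLC/RV is probably a drafting slip.

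The age gap is certain as a matter of text and limited to the optional subgroup analysis. The number of patients concerned cannot be derived from the documents. No sample size or power figure in either document changes.

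**What to change.** In SAP 4.2.8.2 and 4.2.8.3, replace TLC/RV with RV/TLC. In SAP 4.2.8.3, extend the upper age band from 31-65 to 31-75, so that the two bands cover all 58 eligible ages; this keeps the contrast with the 18-30 group. That is two ratio edits and one age-band edit, with no effect on sample size, data collection or trial conduct.
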